### *Secondary outcome*

- Peak plasma cTnI and total cTnI release (area under the curve) during surgery or during the first 4 days after surgery
- Endothelial dysfunction assessed by the non-invasive EndoPat system (24 hours and 72 hours after surgery)
- Perioperative myocardial infarction (Universal definition of myocardial infarction, published in 2012 [15])
  - A typical rise or fall of cTnI with peak plasma cTnI  $\geq 45\text{ng/L}$  (99th percentile URL, 10% CV at 40 ng/L) and with at least one of the following:
    - Symptoms of ischemia
    - New or presumed new significant ST-segment-T wave (ST-T) changes or new left bundle branch block (LBBB)
    - Development of pathologic Q waves in the ECG
    - Imaging evidence of new loss of viable myocardium or new regional wall motion abnormality
    - Identification of an intracoronary thrombus by angiography or autopsy
  - Cardiac death with symptoms suggestive of myocardial ischemia and presumed new ischemic ECG changes or new LBBB, but death occurred

---

 Defined as a preoperative cTnI  $\geq 45\text{ng/L}$  (99th percentile URL, 10% CV at 40ng/L)

before cardiac biomarkers were obtained, or before cardiac biomarker values would be increased.

- Development of new pathologic Q waves on an ECG or pathological findings of a healing myocardial infarction if troponin levels were obtained at times that could have missed the clinical event
- Major adverse cardiovascular events (30 days and one year after surgery)
  - Nonfatal cardiac arrest, coronary revascularization procedure (PCI or CABG), acute coronary syndrome, stroke, congestive heart failure, new clinically important cardiac arrhythmia, peripheral arterial thrombosis, rehospitalization for cardiovascular reasons.
- Length of postoperative hospital stay
- Length of intensive care unit stay
- All-cause mortality (30 days and one year after surgery)
  - cardiovascular or non-cardiovascular (a clearly documented non-cardiovascular cause)

Besides the inclusion and exclusion criteria, the following baseline data and preoperative/postoperative risk factors will be collected from each patient (records):

- Age, sex
- co-morbidities: chronic obstructive pulmonary disease, atrial fibrillation, active cancer

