- Number of patients with peak plasma cardiac troponin I (cTnI)  $\geq$  45ng/L (99th percentile URL, 10% CV at 40ng/L) during surgery or during the first 4 days after surgery (perioperative myocardial injury). If elevated at baseline (preoperative) a 20% or greater increase of cTnI according to baseline is required for the diagnosis of a perioperative myocardial injury [15].
  - o Holstebro Hospital: Number of patients with peak plasma cardiac troponin I (cTnI) > 24 ng/L (99th percentile URL, 14% CV)

*Secondary outcome*

- Peak plasma cTnI and total cTnI release (area under the curve) during surgery or during the first 4 days after surgery
- Plasma N-terminal Pro-Brain Natriuretic Peptide (NT-proBNP) before surgery and at day 1 after surgery.
- Endothelial dysfunction assessed by the non-invasive EndoPat system (24 hours after surgery, only done at Zealand University Hospital)
- Biomarkers of coagulation (only patients included at Holstebro Hospital)
- Perioperative myocardial infarction (Universal definition of myocardial infarction, published in 2012 [15])
  - A typical rise or fall of cTnI with peak plasma cTnI  $\geq$  45ng/L (99th percentile URL, 10% CV at 40 ng/L) (Holstebro cTnI > 24 ng/L), and with at least one of the following:
    - Symptoms of ischemia

---

 Defined as a preoperative cTnI  $\geq$  45ng/L (99th percentile URL, 10% CV at 40ng/L)

- New or presumed new significant ST-segment-T wave (ST-T) changes or new left bundle branch block (LBBB)
  - Development of pathologic Q waves in the ECG
  - Imaging evidence of new loss of viable myocardium or new regional wall motion abnormality
  - Identification of an intracoronary thrombus by angiography or autopsy
- Cardiac death with symptoms suggestive of myocardial ischemia and presumed new ischemic ECG changes or new LBBB, but death occurred before cardiac biomarkers were obtained, or before cardiac biomarker values would be increased.
  - Development of new pathologic Q waves on an ECG or pathological findings of a healing myocardial infarction if troponin levels were obtained at times that could have missed the clinical event
- Major adverse cardiovascular events (30 days, one year and five years after surgery)

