    - Nonfatal cardiac arrest, coronary revascularization procedure (PCI or CABG), acute coronary syndrome, stroke, congestive heart failure, new clinically important cardiac arrhythmia, peripheral arterial thrombosis, rehospitalization for cardiovascular reasons.
  - Length of postoperative hospital stay
  - Length of intensive care unit stay
  - All-cause mortality (30 days, one year and five years after surgery)
    - cardiovascular or non-cardiovascular (a clearly documented non-cardiovascular cause)

Besides the inclusion and exclusion criteria, the following baseline data and preoperative/postoperative risk factors will be collected from each patient (records):

- Age, sex

- co-morbidities: chronic obstructive pulmonary disease, atrial fibrillation, active cancer, autoimmune diseases
- medications (Paracetamol, NSAID, steroid, antibiotics, opioid, ASA, statin, brilique, clopidogrel, anticoagulant medications,  $\beta$ -blocker, calcium antagonist, diuretics, ACE-I, angiotensin antagonist, antiarytmic, nitrate, digoxin, antidiabetics incl. insulin) preoperative and during hospitalization
- preoperative ASA score
- preoperative revised cardiac risk index score
- type and length of surgery
- type and length of anesthesia and type of analgesia
- Intraoperative hypotension (and length) defined as a systolic blood pressure <100mmHg
- Preoperative and postoperative plasma creatinine (incl. eGFR) and plasma hemoglobin
- blood transfusion
- Clinical events during hospitalization according to the Clavien Dindo classification [16, 17] e.g. pneumonia, sepsis, acute respiratory failure, acute kidney failure and lung embolism.

The one and five year follow-up on all included patients will be performed with information (procedure- and diagnosis codes) registered in the Danish National Patients Register (Landspatientsregisteret). Likewise, information on death and cause of death will be deducted from "Dødsårsagsregisteret".

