#### *Participant timeline*

*Intervention:* The remote ischemic preconditioning procedure is carried out immediately after the induction of regional or general anesthesia. The blood pressure cuff is placed on the upper limb. The cuff is inflated to 200 mmHg resulting in a total occlusion of the blood flow to the limb. After 5 minutes of ischemia the cuff is deflated and the limb is reperfused for 5 minutes. The procedure is carried out 4 times in a row. For patients with systolic blood pressures >185 mmHg, the cuff will be inflated to at least 15 mmHg above the patient's systolic blood pressure. The first round should be completed before the initiation of surgery.

The patients will have blood collected to assess cTnI (preoperative and in the morning at days 1, 2, 3 and 4 after surgery) and NT proBNP (preoperative and in the morning at day 1 after surgery). All patients with a cTnI assessment  $\geq 45\text{ng/L}$  will have a minimum of one ECG performed and a medical doctor will evaluate the patient for the presence of an ischemic or non-ischemic event that can explain the elevated cTnI (i.e. sepsis, pulmonary embolism, cardioversion). The medical doctor will determine whether further action should be taken. If necessary, a cardiologist will be consulted. Patient included at Holstebro Hospital will have blood collected for assessment of coagulation biomarkers. The blood samples are taken preoperatively, 2 hours after incision and in the morning at day 1 and 2 after surgery (4 times 6 ml blood).

The investigator observes the patients during their stay in hospital and records the occurrence of any primary or secondary outcomes. The investigator will undertake a short- and long-term follow up (30 days, one and five years after surgery) and record the occurrence of any primary or secondary outcomes. The follow-up will be carried out by reviewing the patients' electronic hospital records, by a personal phone call and with data from the Danish National Patient Register and "Dødsårsagsregisteret".

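### The SAP drops patients who die before a second postoperative troponin from 30-day MACE and mortality; among those analysed, MACE omits fatal arrest and cardiovascular death

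*Combined protocol and SAP*

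**What the plan says.** **Who is analysed.** The final SAP (Definitions of the population) requires at least two postoperative troponins within four days of surgery for both the intention-to-treat and the per-protocol set. The earlier SAP version has the same definitions. No other set is defined, so the secondary comparisons, including 30-day MACE and 30-day all-cause mortality, fall within these two. The current protocol (Withdrawal criteria and dropouts) says otherwise: a patient whose primary outcome is missing is still followed, short and long term, and is included in the final intention-to-treat analysis. Under Participant timeline, the investigator is to "record the occurrence of any primary or secondary outcomes" at 30 days, one year and five years.

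**What counts as MACE.** In the current protocol (Secondary outcome) the components are "Nonfatal cardiac arrest, coronary revascularization procedure (PCI or CABG), acute coronary syndrome, stroke, congestive heart failure, new clinically important cardiac arrhythmia, peripheral arterial thrombosis" and, last, "rehospitalization for cardiovascular reasons". The original protocol has the same list, beginning "Nonfatal cardiac arrest, coronary revascularization procedure (PCI or CABG), acute coronary syndrome". Neither SAP version redefines it.

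**Where death is captured.** All-cause mortality is a separate secondary outcome, divided into "cardiovascular or non-cardiovascular (a clearly documented non-cardiovascular cause"). Cause of death comes from the cause-of-death register: "information on death and cause of death will be deducted from" that source. The final SAP lists all-cause mortality at 30 days but not the cardiovascular split. It plans a chi-square or Fisher test for categorical outcomes and gives no rule for patients who die.

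**The concern.** A troponin requirement makes sense for a troponin outcome. It has no role in deciding who contributes to death or MACE, which can be established from hospital records, "by a personal phone call and with data from the Danish National Patient Register and" the cause-of-death register. Applied to those outcomes, it selects on survival: the earliest deaths leave both numerator and denominator. If the intervention affected early death, the mortality comparison would miss that part of the effect.

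The composition of MACE adds a second, smaller gap. Among analysed patients, an arrest that is survived is an event. The same arrest, if fatal and unaccompanied by another listed event, is not. For this subset the worse outcome gets the better score. Turning a fatal arrest into a survived one raises MACE, and preventing an isolated cardiovascular death leaves it unchanged. With no cardiovascular mortality comparison listed in the SAP, the primary publication has no planned analysis in which cardiovascular death is itself the event.

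**Working it through.** **1. The plan's own figure.** The only sample-size figure is 264 per arm, for 15% versus 7% myocardial injury, two-sided 5%, power 80%.
- Uncorrected: n = [1.96·√(2·0.11·0.89) + 0.8416·√(0.15·0.85 + 0.07·0.93)]² / 0.08² = 238.9, i.e. 239.
- With continuity correction: (238.9/4)·[1 + √(1 + 4/(238.9·0.08))]² = 263.4, i.e. 264.

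It reproduces, and nothing below affects it. The documents give no MACE or death rate, so nothing comparable can be recomputed for those outcomes.

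**2. Timing.** Troponin is taken before surgery and on the mornings of days 1 to 4 (Participant timeline). The second scheduled postoperative sample is therefore on the morning of day 2 at the earliest. A patient who dies before then cannot enter either SAP set.

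**3. Scoring under the text as written, at 30 days.**

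| Patient | In the SAP sets? | MACE | All-cause mortality |
|---|---|---|---|
| Dies before second postoperative troponin | No | not counted | not counted |
| Two troponins, arrest survived | Yes | event | no event |
| Two troponins, fatal arrest, no other listed event | Yes | no event | event |
| Two troponins, isolated cardiovascular death | Yes | no event | event |
| Two troponins, fatal acute coronary syndrome or stroke | Yes | event | event |

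The first row is the conflict with the protocol. The third and fourth rows are the composition gap.

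**4. Size of the analysis-set gap.** Let m be the deaths among 270 evaluable patients in an arm and e the excluded early deaths in that arm. Restoring them raises mortality by (m + e)/(270 + e) − m/270 = e(270 − m)/[270(270 + e)], which is at most e/(270 + e).
- e = 1: at most 1/271 = 0.37 points.
- e = 3: at most 3/273 = 1.10 points.
- e = 5: at most 5/275 = 1.82 points.

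The values of e are assumptions. The between-arm difference shifts only by the imbalance in these terms.

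**5. Size of the composition gap.** One patient is 100/270 = 0.37 points. For k patients in one arm:
- fatal arrest becomes survived arrest: MACE as listed +k/270; MACE or cardiovascular death 0;
- isolated cardiovascular death prevented: MACE as listed 0; MACE or cardiovascular death −k/270.

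For assumed k = 1, 3 or 5 the shift is 0.37, 1.11 or 1.85 points.

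**6. Against sampling error.** The 95% half-width of a difference is 1.96·√[2p(1 − p)/270].
- Assumed MACE rate p = 5%: 3.68 points, or 0.0368 × 270 ≈ 9.9 patients.
- Assumed p = 10%: 5.06 points, or 0.0506 × 270 ≈ 13.7 patients.

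A net 10 to 14 such patients would be needed to match the half-width. This only indicates scale; it does not test whether a conclusion would change.

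**The case against.** The strongest reply is that death is handled elsewhere. All-cause mortality stands beside MACE at the same time points, with a cardiovascular split in the protocol, and a nonfatal-type composite next to a mortality outcome is a common design. This largely stands: the documents do not show that the list is a mistake. The Introduction names vascular death among major cardiovascular complications, but as background, so it does not contradict the endpoint. The reply fails in two places. Patients who die before the second troponin are missing from the SAP's mortality comparison too, and the SAP does not carry over the cardiovascular split.

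A reader might infer that every fatal arrest or cardiovascular death is scored as free of MACE. The documents do not support that. The earliest deaths are excluded, not scored. Acute coronary syndrome, stroke, heart failure and arrhythmia carry no nonfatal limit, so a death attributed to one of them, or an arrest with a recorded arrhythmia, can still count. Some deaths also meet the separate infarction outcome, which includes "Cardiac death with symptoms suggestive of myocardial ischemia and presumed new ischemic ECG changes or new LBBB".

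It can also be said that the analysis set is a separate matter from the composition of MACE. It is a contradiction in its own right and does not depend on the list. The two belong together here because the defence that mortality covers what MACE omits needs mortality to be complete.

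Finally, 270 per arm is the per-protocol target. Intention-to-treat denominators may be larger and the per-patient shift slightly smaller.

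**Conclusion.** The protocol and SAP contradict each other on whether patients without an evaluable primary outcome are analysed. If the SAP is followed, deaths before the second postoperative sample are lost from both 30-day MACE and 30-day mortality. This is the firmer part of the point. Among analysed patients, a fatal arrest or isolated cardiovascular death with no other listed event is scored as free of MACE, so MACE can be interpreted only together with mortality. That part is modest.

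The size is unknown because the documents give no rate for either group. At 270 per arm each patient is about 0.37 points, and the effect is probably small. A reader might infer that the MACE result could become significant or reverse; nothing in the documents supports that. What is affected is the completeness of the two outcomes and the direction in which MACE moves for this subset. The primary outcome and the sample size are untouched. The finding concerns the 30-day comparisons. The protocol uses the same list at one and five years, but the SAP for the primary publication specifies no analysis there.

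**What to change.** 1. In the SAP, analyse 30-day MACE and all-cause mortality in all randomised patients with follow-up, as the protocol already provides. Keep the two-troponin requirement for the troponin outcomes only.
2. Keep the prespecified MACE list and state that it has no death component. Beside it, add a supplementary composite of MACE or cardiovascular death, including fatal cardiac arrest. Report each component and cardiovascular mortality separately. Do the same at one and five years wherever MACE is reported.

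The cost is one analysis-set sentence and one supplementary outcome. No new data are needed, since follow-up and cause of death are already planned. There are two downsides. The added composite overlaps with mortality, which separate reporting of components makes visible. Also, the protocol's wording asks for a clearly documented cause before a death is called non-cardiovascular, so deaths of unclear cause may be classed as cardiovascular and inflate the composite; report those deaths separately. If outcomes have already been unblinded, label the addition post hoc.

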#### *Participant timeline*

*Intervention:* The remote ischemic preconditioning procedure is carried out immediately after the induction of regional or general anesthesia. The blood pressure cuff is placed on the upper limb. The cuff is inflated to 200 mmHg resulting in a total occlusion of the blood flow to the limb. After 5 minutes of ischemia the cuff is deflated and the limb is reperfused for 5 minutes. The procedure is carried out 4 times in a row. For patients with systolic blood pressures >185 mmHg, the cuff will be inflated to at least 15 mmHg above the patient's systolic blood pressure. The first round should be completed before the initiation of surgery.

The patients will have blood collected to assess cTnI (preoperative and in the morning at days 1, 2, 3 and 4 after surgery) and NT proBNP (preoperative and in the morning at day 1 after surgery). All patients with a cTnI assessment  $\geq 45\text{ng/L}$  will have a minimum of one ECG performed and a medical doctor will evaluate the patient for the presence of an ischemic or non-ischemic event that can explain the elevated cTnI (i.e. sepsis, pulmonary embolism, cardioversion). The medical doctor will determine whether further action should be taken. If necessary, a cardiologist will be consulted. Patient included at Holstebro Hospital will have blood collected for assessment of coagulation biomarkers. The blood samples are taken preoperatively, 2 hours after incision and in the morning at day 1 and 2 after surgery (4 times 6 ml blood).

The investigator observes the patients during their stay in hospital and records the occurrence of any primary or secondary outcomes. The investigator will undertake a short- and long-term follow up (30 days, one and five years after surgery) and record the occurrence of any primary or secondary outcomes. The follow-up will be carried out by reviewing the patients' electronic hospital records, by a personal phone call and with data from the Danish National Patient Register and "Dødsårsagsregisteret".

Sample size: A large international cohort study done by the VISION investigator group showed that 8.0% of patients undergoing non-cardiac surgery suffered myocardial injury [4]. In our study we include patients with a moderate – high risk of suffering myocardial injury, while the VISION study included patients at all risk levels. We predict that 15% of the patients in the placebo group will suffer from myocardial injury and that the incidence of myocardial injury will be reduced to 7% in the intervention group. Type I error is set at 5% and type II error is set at 20%. In total 2 x 264 patients need to be included based on this power calculation. We will include patients until we have a total of 2 x 270 patients for evaluation.

#### *Biobank*

We will establish a biobank at Department of Clinical Biochemistry, Holstebro Hospital, containing the drawn plasma for analysis of biomarkers of coagulation and NT-pro-BNP. Only patients included at Holstebro Hospital will have samples drawn for the biobank. In total, a

maximum of 30 ml blood will be drawn from each participating patient (24mL for the coagulation biomarkers and 6 ml for NT-pro-BNP). The blood samples will be centrifuged and only plasma samples will be stored (-80°C). Moreover, a biobank will be established at the Department of Surgery, Zealand University Hospital. Every 4-6 month plasma samples for NT-pro-BNP analysis will transferred securely from the biobank at Holstebro Hospital to the biobank at Zealand University Hospital. All plasma samples will be retained until all analyzes are made and for no more than 10 years. The purpose of the biobank is to make sure that all assessments are made with the same equipment in the lab, hereby reducing variations due to technical variations in the equipment used. All requirements regarding establishment and maintenance of the biobank will be met.

#### *Recruitment*

All patients hospitalized to undergo emergent or urgent major noncardiac surgery at Department of Orthopedic Surgery, Zealand University Hospital, Department of Orthopedic Surgery, Holstebro Hospital, and Department of Orthopedic Surgery, Herlev Hospital, will as far as possible be screened to determine whether they meet the inclusion and exclusion criteria.

#### *Allocation and blinding*

An electronic generator will create the randomization list.

Each patient allocation is randomly selected using sealed opaque envelopes. It is not possible to blind the staff or the patient. Assessor blinding will be performed and the unblinding will take place after final data analysis has been made. An independent data analysis team consisting of a statistician and an external medical scientist will perform interim analysis.

#### *Data collection methods*

##### Blood samples

The blood will be collected from a larger vein (e.g. the cubital vein).

### Plasma cardiac troponin I

Plasma cTnI will be analyzed at the local department of biochemistry using Siemens Healthcare Dimension Vista (Zealand University Hospital, Herlev Hospital), Abbott high-sensitive troponin I (Holstebro Hospital).

### Plasma NT proBNP

Plasma NT proBNP will be analyzed in a standardized manner at the Department of Biochemistry. Samples from Holstebro Hospital will be analyzed as one batch in Region Zealand when all patients have been included. Until then the plasma samples will be stored in a biobank at Department of Biochemistry (Holstebro Hospital) and Department of Surgery (Zealand University Hospital).

### Coagulation biomarkers

The blood is centrifuged and the remaining plasma is stored in the bio-bank at -80°C until further analysis.

### ECG

Trained healthcare professionals using standard ECG equipment will record the ECG.

